8.2.1.5 Sleep Diary

A paper sleep diary will be completed by each subject's LAR/caregiver, on behalf of the subject. Endpoints assessed by the sleep include how long it took the subject to fall asleep

(sleep onset latency [SOL]), the amount of time the subject was awake during the night (WASO), the total amount of sleep obtained (total sleep time [TST]), daytime sleepiness, defined as duration of napping in the daytime, and number of times subject woke up at night. The sleep diary will be completed each day during the 7 days immediately preceding each clinic visit after screening.

Sleep Parameters	Derivation
Sleep Onset Latency (SOL) in minutes	[First night: time to sleep – time subject went to bed) + (Second night: time to sleep – time subject went to bed) + (Third night: time to sleep – time subject went to bed) + (Fourth night: time to sleep – time subject went to bed) + (Fifth night: time to sleep – time subject went to bed) + (Sixth night: time to sleep – time subject went to bed) + (Seventh night: time to sleep – time subject went to bed)]/7 (or number of days with non-missing values) Note: For sleep time, consider the time closest on or after the time the subject went to bed on the same day
WASO (minutes)	Sum (time to sleep – time to wake from the previous log), considering all records between the time subject went to bed until subject woke up, then take the weekly average using the number of days with non-missing values.
TST (hours)	The weekly average, using the number of days with non-missing values, of total sleep time, converting the unit into hours.
Daytime Sleepiness (minutes)	The weekly average, using the number of days with non-missing values, of (time to sleep – time to wake), considering only records on the same day before subject went to bed
Number of times subject woke in the nights (counts)	The weekly average, using the number of days with non-missing values, of number of records from WASO considering all records between the time subject went to bed until subject woke up.

Weekly average of sleep parameters will be calculated with missing data excluded.

The baseline values of actigraphy parameters will be obtained from data collected within 7 days immediately preceding Day 1.

Change from baseline on the sleep parameters at Week 2, Week 6, and Week 12 will be analyzed as described in [Section 8.1](#).

Missing data convention from the provider will be used for missing assessments and scores. Otherwise, missing data from the assessment will be kept as missing.

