5.2 Treatments Administered

Subjects will take all doses orally (assisted by an LAR/caregiver, if necessary) TID (morning, afternoon, evening), at approximately the same times each day, for the duration of the 12-week treatment period. The morning and afternoon doses should be taken with light low-fat food (a glass of low-fat milk would qualify as food), and the afternoon dose should be taken at least 6 hours after the morning dose. The evening dose should be taken 30 minutes before bedtime. Capsules may be opened and the contents sprinkled onto 1 teaspoon of low-fat semiliquid food (eg, applesauce, yogurt, pudding) for ingestion, but this approach must be followed consistently throughout the study. The capsule contents must not be placed directly in liquid. The LAR/caregiver must document specifically how each capsule was taken (eg, swallowed whole or taken in 1 teaspoon of semiliquid food).

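### The same-day condition in the sleep-diary onset-latency rule can drop nights on which bedtime is before midnight and sleep begins after it

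*SAP*

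**What the plan says.** SAP section 8.2.1.5 derives diary SOL night by night over seven nights. A typical term is "Second night: time to sleep – time subject went to bed". The sum is divided by 7, "or number of days with non-missing values". The attached note picks the sleep time to use: "Note: For sleep time, consider the time closest on or after the time the subject went to bed on the same day". Below the table the SAP adds: "Weekly average of sleep parameters will be calculated with missing data excluded".

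Other rows of the same table set their windows differently:

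- **WASO:** the row works by "considering all records between the time subject went to bed until subject woke up, then take the weekly average". That window crosses midnight without difficulty, and the row for number of night wakings uses the same one.
- **Daytime sleepiness:** the row averages sleep records, "considering only records on the same day before subject went to bed".

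No passage says whether a day is a calendar date or a diary night, and none covers the crossing of midnight. The results feed the planned modelling: "Change from baseline on the sleep parameters at Week 2, Week 6, and Week 12 will be analyzed as described in" SAP section 8.1. Diary SOL is a named exploratory endpoint (Protocol 7.3.1, SAP 3.2.3.1).

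**The concern.** A programmer with date-stamped records could apply the SOL note by calendar date. A subject who goes to bed at 23:20 and falls asleep at 00:30 has a latency of 70 minutes, but no sleep time on the date of that bedtime. The night becomes missing and the divisor falls by one, so nothing in the output shows the loss.

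For any bedtime before midnight, whether the night survives depends on how long the subject took to fall asleep, so the missingness depends on the outcome. If latencies shorten on treatment, fewer nights are lost after baseline than at baseline, and the two means are taken over differently selected nights.

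There is no placebo group, so changes from baseline and differences between regimens are the only evidence on this endpoint. The SAP also plans to compare diary with actigraphy. Actigraphy SOL runs from the start of the rest period with no day limit (SAP 8.2.3.1), so part of any disagreement between the two could come from this rule alone.

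**Working it through.** The documents state no figure for diary SOL, so there is none to reproduce. The check has three parts.

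**1. Which nights are lost under the calendar-date reading.** With bedtime B and latency L, a night is lost when B is before 24:00 and B + L is at or after 24:00, that is, when L ≥ 24:00 − B.

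| Bedtime | Sleep onset | Latency (min) | Outcome |
|---|---|---|---|
| 23:00 | 00:30 | 90 | lost |
| 23:50 | 00:05 | 15 | lost |
| 20:30 | 23:30 | 180 | kept |
| 00:20 | 01:50 | 90 | kept |

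The cut-off is the time left until midnight, not a fixed latency. Long latencies are more likely to be lost, but a short one can go and a long one can stay. A late onset is kept if bedtime was also after midnight.

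**2. How large the bias could be.** Bedtimes, latencies and effect size are all assumed, because the documents give none.

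*Set A.* Bedtime is normal with SD 1 h and mean 21:30 to 23:00. SOL is lognormal with log-SD 0.7, capped at 300 min. Treatment shortens it by one third and bedtimes do not move.

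| Median SOL at baseline | Baseline nights lost | Share of true reduction retained |
|---|---|---|
| 30 min | 4–20% | 74–86% |
| 60 min | 16–39% | about 56–64% |

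For example, with mean bedtime 22:00 and median 60 min, the true baseline mean is 75.7 min and the rule gives 57.8. A true improvement of 24.8 min appears as 14.6 min (14.6/24.8 = 59%).

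*Set B.* Bedtime SD is 45 min. SOL is lognormal with log-SD 0.8 and no cap, and the median falls from 45 to 30 min. The mean of a lognormal is median × exp(log-SD²/2). This gives 45 × exp(0.32) = 62.0 min at baseline and 30 × exp(0.32) = 41.3 min on treatment, a true change of −20.7 min (−20.6 to −20.8 as simulated).

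| Mean bedtime | Baseline nights lost | Baseline mean under the rule (min) | Observed change (min) | Share of true change |
|---|---|---|---|---|
| 20:30 | 3.5% | 54.8 | −15.6 | 76% |
| 21:30 | 9.3% | 49.6 | −12.8 | 62% |
| 22:30 | 26.0% | 42.3 | −9.9 | 48% |
| 23:15 | 39.5% | 42.0 | −11.4 | 55% |

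A true worsening from 30 to 45 min is attenuated by the same proportions.

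Now keep the median at 45 min, so that SOL does not change, and move the mean bedtime from 22:30. Bedtimes 60 min earlier produce a false change of +7.4 min. Bedtimes 60 min later produce +3.1 min, because more bedtimes then fall after midnight and those nights are kept.

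**3. The daytime-sleepiness row.** Suppose a subject wakes in the night, falls asleep again at 02:40 and wakes at 07:00. By calendar date this record lies before that evening's bedtime, so it meets the row's condition. Counted as a nap it adds 260 min to that day, and one such day in a complete week adds 260/7 = 37 min to the weekly average. Yet the SAP defines this endpoint as daytime napping.

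**The case against.** The strongest reply is that the note was never meant by calendar date. The SOL formula is written night by night, and each term pairs one night's bedtime with that night's sleep time. The neighbouring rows already run from bedtime to waking. In that company the note can mean the first sleep entry at or after bedtime for that diary day, which stops an earlier nap being picked up. The same-day words may also attach to the bedtime and not to the sleep time. On a diary-night reading no night is lost and there is no bias. The diary form, which might settle it, is not in the documents. This stands: the loss is possible, not established. But the note uses different words from the window in its own table, and the two readings give different results.

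A reader might also infer more than the documents support:

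- **That every onset after midnight is lost, or exactly the longest latencies.** The worked nights show that neither is so.
- **That any drug effect must shrink.** This depends on bedtimes staying stable, and the bedtime-shift results show a false change where SOL did not move.
- **That the contrast between regimens is attenuated.** Protocol 5.2 states "The evening dose should be taken 30 minutes before bedtime", and that capsule is active only in the 10 and 15 mg/day arms. But the documents do not say that diary SOL should differ by regimen, those two arms share the same evening capsule, and the figures here concern change from baseline only.
- **That night sleep will be counted as napping.** The SAP's definition of daytime sleepiness speaks against it. Only the derivation row, read by calendar date, allows it.

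Finally, the stakes are modest. The endpoint is exploratory, no efficacy power was planned, p-values are treated as exploratory (SAP 11.1), and actigraphy SOL and the CSHQ sleep-onset item cover the same ground.

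**Conclusion.** The note is a real specification defect of limited consequence. Followed by calendar date, it discards nights that straddle midnight, lowers mean SOL, usually attenuates a change from baseline when bedtimes are stable, and can produce a false change when they move. The illustrative size under Set A is 4–39% of baseline nights lost and about 56–86% of a true one-third reduction retained; Set B goes as low as 48%. These figures rest entirely on the assumed bedtimes and latencies and show plausible scale only. The documents support neither a claim that nights will certainly be lost nor a claim that the bias always runs toward zero. The point is worth acting on because two defensible readings of one derivation rule lead to different endpoint values, and settling it costs very little.

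**What to change.** In SAP section 8.2.1.5:

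1. Remove the same-day condition from the SOL note. Define SOL on date-times for each diary night as the interval from bedtime to the first sleep onset at or after bedtime and before final waking, with the date carried over midnight. This is the window that the WASO row already uses.
2. Define naps in the daytime-sleepiness row as sleep records after final waking and before the next bedtime. A noon-to-noon day would be a weaker choice, since a late-morning nap would fall in the same period as the preceding night.
3. Report the number of nights without a valid SOL by visit and regimen.

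The cost is one sentence for the SOL rule, a matching edit to the nap row, a date rule in the program and a small count table. No new data are needed.

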8.2.3 Direct Subject Assessment Endpoints

8.2.3.1 Actigraphy

Actigraphy is a noninvasive method of monitoring human rest/activity cycles. A small actigraph unit is worn to measure daytime and sleep activity. The actigraph unit stores motion data by clock time, and the data must be uploaded to an actigraphy database for analysis. The actigraphy data (including parameters such as: SOL, WASO, TST, NA, sleep efficiency, daily activity level, and sleep fragmentation) will be compared to the sleep diary data. The derivation of these parameters will be as follows:

Sleep Parameters	Derivation
Sleep Onset Latency (SOL)	Mean of Onset Latency (minutes), duration from the beginning of the rest period to the start of sleep onset, reported when interval type = sleep
Total Sleep Time (TST) during night	Take Sum of sleep time (minutes) where interval type = 'sleep' within each day then the Mean of this sum for an average score per day. Convert its unit to hours in analysis.
Total Sleep Time (TST) during day	Take Sum of sleep time (minutes) where interval type = 'Active' within each day then the Mean of this sum for an average score per day. Convert its unit to hours in analysis.

Wake After Sleep Onset (WASO)	Mean of WASO when interval type = sleep
Nocturnal Awakenings (NA)	Mean of # Wake bouts when interval type = sleep
Sleep Efficiency	Mean of Efficiency (%) when interval type = sleep. Efficiency is defined as total sleep time as a fraction of the rest period (total time in bed).
Daily Activity Level	Take Sum of Total AC (counts) within each day then the Mean of this sum for an average score per day
Sleep Fragmentation	Sum of Fragmentation (%+%) when interval type = sleep

The baseline values of actigraphy parameters will be obtained from data collected within 7 days immediately preceding Day 1.

The change from baseline in the subject actigraphy parameters will be analyzed for Week 2, Week 6, and Week 12, as described in [Section 8.1](#).

Missing data convention from the provider will be used for missing assessments and scores. Otherwise, missing data from the assessment will be kept as missing.

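### Two exploratory sleep derivations in the SAP are wrong as written: diary nap duration has its sign reversed, and actigraphy fragmentation is never averaged over nights

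*SAP*

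**What the plan says.** **Diary naps.** SAP 8.2.1.5 lists among the diary endpoints "daytime sleepiness, defined as duration of napping in the daytime, and number of times subject woke up at night"; Protocol 7.3.1 gives the same definition of daytime sleepiness. The derivation table, in minutes, takes the weekly average of "time to sleep – time to wake), considering only records on the same day before subject went to bed". In the same table, WASO is "Sum (time to sleep – time to wake from the previous log", and sleep onset latency is the time of falling asleep minus the time of going to bed. The section then states: "Change from baseline on the sleep parameters at Week 2, Week 6, and Week 12 will be analyzed". SAP section 4 defines change as the post-baseline value minus the baseline value.

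**Actigraphy fragmentation.** SAP 8.2.3.1 derives this as "Sum of Fragmentation (%+%) when interval type = sleep". Its neighbours are worded differently. WASO is "Mean of WASO when interval type = sleep", and daily activity is "Take Sum of Total AC (counts) within each day then the Mean of this sum for an average score per day". The table also has a row for "Total Sleep Time (TST) during day", and the section says the actigraphy results will be compared with the diary. Seven days of wear are planned before each clinic visit after screening (SAP 3.1; SAP 14.2, note j).

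**The concern.** The nap formula contradicts its own definition. A duration cannot be negative, yet subtracting the end of a nap from its start always gives a negative number. Followed literally, more napping is reported as less, in every summary, model estimate and plot for this endpoint. Direction is what a reader would want from it, since Protocol 1.4 lists somnolence among the common adverse events that exceeded placebo.

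The fragmentation row leaves the programmer to decide how nights are combined. If nights are added up, a subject who wears the device for fewer nights appears to sleep with less fragmentation. Unlike a negative nap, such a value does not look impossible and could pass unnoticed.

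**Working it through.** The SAP states no figure that depends on these rules, so there is none to reproduce. The check applies each formula literally. Clock times, nap lengths, the dose difference and fragmentation values are assumed for illustration; the formulas and the 7-night plan come from the documents.

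**1. Is the dash a subtraction?** Yes, as the neighbouring rows show.
- Sleep onset latency, in bed 21:00 and asleep 21:30: 21:30 - 21:00 = +30 min. Correct.
- WASO, awake 02:00 and asleep again 02:20, with the wake time taken from the preceding record: 02:20 - 02:00 = +20 min awake. Correct.
- Nap, asleep 14:00 and awake 15:00, same record: 14:00 - 15:00 = -60 min. Wrong sign.

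Borrowing WASO's pairing with the preceding record does not rescue the nap row. A 07:00 wake and a 14:00 nap give 14:00 - 07:00 = 420 min, which is time awake. The row states no absolute value.

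**2. Effect on change from baseline (post minus baseline).**

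| Assumed naps, min/day | As written | Correct |
|---|---|---|
| 60 falling to 30 | (-30) - (-60) = +30 | 30 - 60 = -30 |
| 20 rising to 60 | (-60) - (-20) = -40 | 60 - 20 = +40 |

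In the second row the error is 40 - (-40) = 80 min. Because every value changes sign, estimates and limits are mirrored and interval widths are unchanged. An assumed true dose difference of +15 min (95% CI 5 to 25) would be reported as -15 (-25 to -5).

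**3. Fragmentation against the rest of its table.**

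| Rows in SAP 8.2.3.1 | Rule |
|---|---|
| Sleep onset latency, WASO, nocturnal awakenings, efficiency | Mean |
| Night TST, day TST, daily activity | Sum within day, then mean |
| Sleep fragmentation | Sum only |

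Seven of the eight rows end in a mean.

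**4. Size if the sum runs over nights.** With constant fragmentation f per night, the change is f × (n_post - n_base). As a percentage this is (n_post - n_base) / n_base, which does not depend on f. With f = 30:

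| Nights, baseline then later | Sums | Apparent change | True change |
|---|---|---|---|
| 7, 7 | 210, 210 | 0% | 0 |
| 7, 6 | 210, 180 | -30/210 = -14.3% | 0 |
| 7, 5 | 210, 150 | -60/210 = -28.6% | 0 |
| 5, 7 | 150, 210 | +60/150 = +40.0% | 0 |

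The direction can also reverse. If fragmentation truly worsens from 30 to 40 per night while nights fall from 7 to 5, the sum goes from 30 × 7 = 210 to 40 × 5 = 200, a change of -10. The mean rises by 10.

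**5. If (%+%) means two percentages added within one interval,** the row says nothing about combining nights, and no size can be given.

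**The case against.** On naps, the sign error itself is not in dispute; the argument is about consequence. The intended quantity is clear, negative durations would be obvious in listings, and a programmer would probably reverse the subtraction. Other information on sleepiness is unaffected: the CSHQ has its own daytime sleepiness domain (SAP 8.2.1.4), and unacceptable somnolence at clinic visits is reported as an adverse event. Protocol 1.4 also says the non-insomnia studies saw no adverse events at 5 mg, the individual dose used here. The actigraphy daytime row is sleep scored within active intervals, in hours, and is not called napping, so the conflict between the two sources is secondary. All of this stands. It lowers the stakes but does not make the formula right, and a correction made after data are seen is an unplanned departure from the SAP.

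On fragmentation, SAP 8.2.1.5 has a general sentence that sleep parameters are averaged over the week, followed by one on actigraphy baselines, so a programmer might carry the average across. That sentence sits in the diary section, however, and the other seven actigraphy rows each state their own averaging. The within-interval reading of (%+%) is possible, and the percentages above would then not apply. Against it, parentheses elsewhere in the table give units, which fits a sum over sleep intervals. Two further points limit the size. Staff must confirm the actigraph recorded properly before randomization (Protocol 6.1.2), which makes a short baseline less likely. Subjects with no recording contribute no value. Partial wear remains possible, because Protocol 6.3.3.1 keeps subjects in the study who cannot follow the wear guidelines.

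**Conclusion.** Both points hold. The nap derivation is wrong as written: it yields minus the nap length, so every change and regimen difference has the opposite sign with its magnitude unchanged. The fragmentation derivation lacks a stated average on either reading. If summed over nights, it produces a spurious change equal to the relative change in nights recorded, for example -14%, -29% or +40% for 7 to 6, 7 to 5 and 5 to 7 nights; with equal nights the spurious change is zero. The minutes and the 30 per night are assumed, but the sign reversal and the percentages do not depend on them. Both endpoints are exploratory and efficacy was not powered (SAP 11.1). The primary safety endpoints and the sample size are untouched. The correction is still worth making, because it is cheap and avoids a choice made with data in view.

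**What to change.** In SAP 8.2.1.5, derive daytime sleepiness as time to wake minus time to sleep for each nap, summed within each day, then averaged over days with non-missing values. The same line should say whether a day with no nap counts as zero or as missing, which the SAP leaves open. Zero gives napping per day; missing gives nap length on nap days only.

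In SAP 8.2.3.1, derive sleep fragmentation as the mean fragmentation index over recorded sleep intervals. If (%+%) denotes two percentages added within an interval, say so, and then take the mean.

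The cost is two corrected lines and the matching programming, with no new data.

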8.2.2 Clinician-Completed Endpoints

8.2.2.1 Caregiver Top 3 Concerns Visual Analog Scale

In Part 1 of the visual analog scale (VAS), LARs/caregivers will generate their top 3 FXS-associated concerns for the subject and rate these 3 concerns using a 10-cm visual analog scale, with troublesome behaviors anchored at one end with the descriptor “worst ever” and at the other end with the descriptor “no problem at all”. The investigator will then map each LAR/caregiver-generated concern onto one of the predefined FXS domains (i.e. Anxiety, ADHD, Repetitive/Stereotypic Behavior, Disruptive Behavior, Communication, Activities of Daily Living, or Socialization and Other) to which each behavior or symptom applies. The top 3 FXS-associated concerns selected at Baseline will be fixed and assessed at Week 2, Week 6 and Week 12.

Part 2 of VAS will be used to rate three FXS-specific domains: Speech and Communication, Socialization, and Cognition.

At a single visit, it is possible that one subject could have more than one concerns within one domain as these are based on parent report. In this case, the averaged value within one FXS-specific domain per subject will be applied in analysis.

Change from baseline in 1) value of the top 3 FXS-associated concerns, in 2) value of FXS domains after mapping of concerns, and in 3) FXS-specific domains (Speech and Communication, Socialization, Cognition) for the subject will be summarized by Week 2, Week 6, Week 12, as described in [Section 8.1](#).

Missing data convention from the provider will be used for missing assessments and scores. Otherwise, missing data from the assessment will be kept as missing.

